Pulsed field ablation (PFA) is an emerging ablative energy. The basis for the damage effect of ablation is the voltage difference between the inside and outside of the membrane formed by the high-voltage electric field. This is electric field-dependent, does not generate heat locally, and has strong penetration ability. Under the action of high-voltage electric fields, the damage threshold of different tissues is different. The damage is selective to a certain extent, and it is safer for fragile adjacent tissues such as blood vessels, esophagus, and nerves^{9,10}. Currently, other energy forms used for ablation are not selective for this tissue type. In the global key study, the incidence of unsafe events for the product submitted this time was 0.7%, and no complications such as left atrial-esophageal fistula, pulmonary vein stenosis, myocardial infarction, phrenic nerve palsy, and

coronary spasm occurred. The extremely low incidence of unsafe events demonstrates the excellent safety of the product. Compared with existing technologies, the efficiency of PFA energy may also be improved. PFA delivery is completed in a few milliseconds, which may reduce isolation time and the entire operation time. By reducing the total operation time, the anesthesia time and the time the patient and doctor are exposed to radiation are reduced, which greatly improves the efficiency of the operation^{11,12}. The PulseSelect™ pulsed field ablation system is a ring electrode with a central support. Compared with a point-shaped radiofrequency catheter, it isolates the pulmonary veins by ablating a whole circle of 9 electrodes at the same time, further improving the efficiency of the operation. Due to the uniqueness and safety of its energy, it can significantly reduce postoperative complications and hospitalization time, shorten the patient's recovery period, and reduce the need for secondary treatment, thereby effectively reducing the patient's medical costs and economic burden¹³. The results of the Pulsed AF study also showed that at 6 and 12 months after surgery, the overall quality of life of patients (AFEQT and EQ-5D) increased by 5 points and 0.03 points respectively compared with the baseline level, and the results were statistically significant¹⁴. It can be seen that PFA reduces the overall medical resource investment by reducing the re-ablation rate and cardiovascular events.

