3.1 Sample size estimation

After literature search, the literature mainly reported that the scale used for QoL endpoints was AFEQT, and some used the MLHFQ scale. Therefore, the scoring results of the AFEQT scale are summarized as follows.

1. CABANA study

a) The CABANA study compared the effects of medication and catheter ablation on quality of life, and conducted long-term (60 months) AFEQT and MAFSI scales. The population accounted for 946 (42.9%) paroxysmal atrial fibrillation, 1042 (47.3%) persistent atrial fibrillation and 215 (9.8%) long-term persistent atrial fibrillation. The proportion of heart function Class II/III was 776 (35.5%), and the proportion of ejection fraction $\leq 35\%$ was 69 (4.5%).

b) The AFEQT scores for catheter ablation and medical therapy at 3 months were 79.8 (18.6) vs. 76.5 (20.4), and 12 months were 86.4 (16.5) vs. 80.9 (18.5). If the sample calculation is based on the above reference.

i. Based on the AFEQT score at 3 months, the two groups had 550 samples respectively.

Numeric Results for an Unequal-Variance T-Test
 $\delta = \mu_1 - \mu_2$
Hypotheses: H0: $\delta = 0$ vs. H1: $\delta \neq 0$

Target Power	Actual Power	N1	N2	N	μ_1	μ_2	δ	σ_1	σ_2	Alpha
0.8	0.80042	550	550	1100	79.8	76.5	3.3	18.6	20.4	0.05

ii. Based on the AFEQT score at 12 months, the two groups had 161 samples respectively

Numeric Results for an Unequal-Variance T-Test
 $\delta = \mu_1 - \mu_2$
Hypotheses: H0: $\delta = 0$ vs. H1: $\delta \neq 0$

Target Power	Actual Power	N1	N2	N	μ_1	μ_2	δ	σ_1	σ_2	Alpha
0.8	0.80142	161	161	322	86.4	80.9	5.5	16.5	18.5	0.05

2. CABANA sub-study heart failure cohort

a) Paroxysmal atrial fibrillation (AF) accounted for 31.6%, persistent AF accounted for 55.3%, and long-term persistent AF accounted for 13.1%. 79% of patients had a left ventricular ejection fraction (EF) $\geq 50\%$, 11.7% had an EF between 40% and 49%, and 9.3% had an EF $< 40\%$.

b) The scores for catheter ablation and medical therapy at 12 months were 80.6 (19.8) and 75.0

(19.6). If the sample calculation is based on the above reference, 196 patients are needed in each group.

Numeric Results for an Unequal-Variance T-Test

$$\delta = \mu_1 - \mu_2$$

Hypotheses: H0: $\delta = 0$ vs. H1: $\delta \neq 0$

Target Power	Actual Power	N1	N2	N	μ_1	μ_2	δ	σ_1	σ_2	Alpha
0.8	0.80154	196	196	392	80.6	75	5.6	19.8	19.6	0.05

3. CAPLA study

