1、 The AFEQT value of the endpoint of the pulse catheter ablation group be selected from the

CABANA heart failure cohort at 12 months, which is 80.6 (19.8). Referring to the KiCS-AF cohort study, which divided the AFEQT improvement value into three levels of 5, 10 and 15, we set the AFEQT value of the drug treatment group to 75.6/70.6/65.6.

2、 Set the AFEQT of the drug group to 75.6, $\alpha=0.05$, $\beta=0.2$, and 248 patients are required in each group.

Numeric Results for an Unequal-Variance T-Test

$$\delta = \mu_1 - \mu_2$$

Hypotheses: $H_0: \delta = 0$ vs. $H_1: \delta \neq 0$

Target Power	Actual Power	N1	N2	N	μ_1	μ_2	δ	σ_1	σ_2	Alpha
0.8	0.80138	248	248	496	80.6	75.6	5	19.8	19.8	0.05

3、 Set the AFEQT of the drug group to 70.6, $\alpha=0.05$, $\beta=0.2$, and 63 cases are needed in each group. Considering a dropout rate of 20%, 79 cases are needed in each group.

Numeric Results for an Unequal-Variance T-Test

$$\delta = \mu_1 - \mu_2$$

Hypotheses: $H_0: \delta = 0$ vs. $H_1: \delta \neq 0$

Target Power	Actual Power	N1	N2	N	μ_1	μ_2	δ	σ_1	σ_2	Alpha
0.8	0.80306	63	63	126	80.6	70.6	10	19.8	19.8	0.05

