3.6 Elimination criteria

The criteria for subject exclusion include, but are not limited to: misdiagnosis; no examination or observation records;

The reasons for exclusion should be stated, and no statistical analysis of efficacy will be performed; if the patient receives treatment and has at least one safety record, he or she may participate in the safety analysis depending on the situation.

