3.7 Criteria and procedures for stopping the trial/trial treatment

The criteria for stopping the study/trial treatment include, but are not limited to:

- (1) The subject withdraws from the trial;
- (2) Unexpected serious adverse events of the device occur, causing serious danger to the subjects participating in the study;
- (3) The medical device regulatory authority or ethics committee requires the trial to be stopped;
- (4) Other circumstances that require the trial/trial treatment to be stopped;

Procedures for Discontinuation of Study/Study Treatment:

- (1) Subjects withdraw from the study: Regardless of the reason, the records of cases withdrawing from the study should be retained, and the last evaluation and examination results should be carried forward as the final results, and the full data set analysis should be conducted on their efficacy and safety. The study conclusions and reasons for the withdrawal of all cases should be recorded;

(2) Ethics Committee requires the study to be stopped: For ethical and scientific reasons, the ethics committee requires the study to be stopped. After the researcher learns of the situation, the researcher should stop the study in a timely manner and keep the communication records or written documents of the study cessation;

(3) Regulatory agency requires the study to be stopped: If the medical device supervision and management department requires the study to be stopped, the person in charge of the study should notify each research unit in writing in a timely manner after learning of the situation;

(4) Other situations where the study/research treatment must be stopped: The situation where the subject stops the study/research treatment due to illness or other reasons should be recorded in detail; the cessation of the entire study should be reported to each research unit in writing in a timely manner; other situations where the study/treatment must be stopped should also be recorded in detail.

4. Study plan

4.1 Treatment of patients in the drug group:

Patients who enter the drug group after screening can receive electrical cardioversion or drug cardioversion for drug treatment. If the patient undergoes electrical cardioversion, preoperative examinations must be completed before surgery to exclude surgical contraindications.

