The following information should be collected/completed at the $6m \pm 15d$ follow-up after surgery:

- ◆ Vital signs
- ◆ Standard electrocardiogram
- ◆ Holter
- ◆ AFEQT quality of life score for patients with atrial fibrillation
- ◆ Cardiac ultrasound
- ◆ Medication status
- ◆ Adverse events & serious adverse events

(7) V8 12 months post-surgery

The following information should be collected/completed at the $12m \pm 15d$ follow-up after surgery:

- ◆ Vital signs
- ◆ Laboratory tests
- ◆ Standard electrocardiogram
- ◆ Holter
- ◆ AFEQT quality of life score for patients with atrial fibrillation
- ◆ Cardiac ultrasound

- ◆ Medication status
- ◆ Adverse events & serious adverse events

Note: Medication status: Record the medication status during the study period (from signing the informed consent to the end of follow-up). Routine solution preparation (normal saline, glucose solution), intraoperative anesthetics, and intraoperative anticoagulants do not need to be recorded. Drugs used for corrective treatment of adverse events also need to be recorded.

Adverse events: Record clinically significant adverse events of the subjects from signing the informed consent to the end of follow-up. Events in which the health status of the subjects does not deteriorate seriously due to planned hospitalization for existing diseases or follow-up required by the protocol are not recorded as serious adverse events.

5. End point

5.1. Primary endpoint:

Change in quality of life at 12 months as measured by the Atrial Fibrillation Quality of Life Survey (AFEQT). Improvement in quality of life from baseline to 12 months after pulsed field ablation procedure or AAD as measured by the Atrial Fibrillation Quality of Life Survey (AFEQT), with values ranging from 20 - 140 (higher scores mean worse outcomes).

5.2 Secondary endpoint:

- (1) The rate of atrial fibrillation-free recurrence during clinical follow-up within 12 months after surgery, that is, the success rate of pulsed field therapy for AF (including atrial tachycardia (AT) lasting more than 30 seconds, atrial flutter (AFL), and AF endpoint events);
- (2) Complications and adverse events during the pulsed field ablation surgery and during the postoperative follow-up, including readmission, cardiovascular events, cardiovascular death, all-cause death, and also including serious adverse events related to the surgery.
- (3) Rehospitalization due to heart failure or recurrence of atrial fibrillation 3 months after surgery;

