- (4) The incidence of AT/AF/AFL events 3 months later.;
- (5) Improvement of cardiac function 6 and 12 months after surgery, including echocardiogram E/e', proBNP, etc.

6. Methods and timing for evaluating, recording and analyzing safety parameters

- (1) Record the occurrence of death, stroke or transient ischemic attack of the subjects during the study;

(2) Surgical operation-related parameters (operation time, left atrial operation time, number of ablation discharges, X-ray exposure time and X-ray radiation, etc.) and intraoperative complications: Observe and record the occurrence of surgery-related adverse events from the beginning to the end of the surgery. All adverse events should be tracked and followed up until they return to normal or baseline, or are sufficient to explain the abnormality. If the subject's participation in this trial ends, it should be tracked until the last follow-up;

(3) Clinically significant vital signs and related examinations:

Vital signs: Vital signs should be checked during the screening period, 1, 2, 3, 6 and 12 months of outpatient follow-up, and observed and recorded;

Laboratory examination: blood routine, blood biochemistry, coagulation function, electrolytes, coagulation function, NT-proBNP, D-dimer, myocardial enzyme spectrum and high-sensitivity cardiac troponin I are performed during the follow-up period. When clinically significant abnormal laboratory test results are found, they should be re-examined and followed up until they return to normal or have no clinical significance or baseline status; relevant laboratory tests need to be completed before the patient is discharged;

Standard electrocardiogram: 12-lead surface electrocardiogram is performed during the screening period, 1, 3, 6 and 12 months of follow-up;

Holter is used for follow-up at 3, 6 and 12 months after surgery.

Echocardiogram: The investigator may choose to perform transthoracic echocardiogram or/and transesophageal echocardiogram according to the patient's condition;

AFEQT Atrial Fibrillation Patient Quality of Life Scale: The patient's quality of life is scored during the screening period and 1, 3, 6 and 12 months after surgery;

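### Section 3.7 fixes last-observation-carried-forward for all withdrawn subjects, although the protocol's own CABANA means show AFEQT still changing after month 3, by different amounts in the two groups

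*Protocol*

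**What the plan says.** Section 3.7 of the protocol, under the procedures for subjects who withdraw, keeps their records regardless of the reason. It then states that "the last evaluation and examination results should be carried forward as the final results", and that "the full data set analysis should be conducted on their efficacy and safety". This is an imputation rule for efficacy, with no exception by reason or time of withdrawal. The statistical section (section 9) names no other way of handling missing data.

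Section 3.6 defines a separate category, eliminated subjects, for whom "no statistical analysis of efficacy will be performed".

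The primary endpoint (section 5.1) is AFEQT change from baseline to 12 months. Section 6 says that "quality of life is scored during the screening period and 1, 3, 6 and 12 months after surgery", so a carried score could come from screening or from month 1, 3 or 6. Section 4.3 also lists a score before discharge, which section 6 and the flow chart do not.

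The sample size text (section 3.1) ends with "Considering a dropout rate of 20%, 79 cases are needed in each group". It does not divide the 20% by group, time or reason.

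**The concern.** Carrying the last score forward gives an unbiased 12-month group mean only if the mean score of those who leave would not have changed afterwards. Section 3.1 contains figures that speak against this: "The AFEQT scores for catheter ablation and medical therapy at 3 months were 79.8 (18.6) vs. 76.5 (20.4), and 12 months were 86.4" with ablation, against 80.9 with drug. Both groups improve after month 3, and by different amounts.

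The 12-month contrast is therefore biased by an amount that depends on how many subjects leave each group and when. The comparison is an open cohort study of a procedure against drug treatment, with no randomisation described, so dropout could well differ between groups. Carried scores are also treated as observed 12-month data, which makes the result look more precise than it is.

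If the clause were also applied to 12-month freedom from recurrence, which section 3.7 does not spell out, a subject who left without a recorded event would count as recurrence-free for the full year.

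**Working it through.** **The plan's own figures.** For a difference of 80.6 − 70.6 = 10, SD 19.8 in both groups and two-sided alpha 0.05, the unequal-variance t-test with 63 per group has power 0.80306, as stated in section 3.1. Allowing for dropout, 63 / 0.8 = 78.75, so 79 per group. The planned standard error with 63 completers per group is 19.8 × √(2/63) = 3.53.

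**Change after month 3 (CABANA means, section 3.1).**
- Ablation: 86.4 − 79.8 = +6.6
- Drug: 80.9 − 76.5 = +4.4
- Group difference: 79.8 − 76.5 = 3.3 at month 3; 86.4 − 80.9 = 5.5 at month 12

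Higher is read as better, as section 3.1 uses the scores. Section 5.1 states the opposite direction, "with values ranging from 20 - 140 (higher scores mean worse outcomes"; that conflict does not affect the argument here.

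**Month-3 scores carried forward.** If those who leave would have followed their group mean, the expected result is

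5.5 + 4.4 × (drug dropout) − 6.6 × (ablation dropout).

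| Ablation / drug dropout (assumed) | Calculation | Result | Shift |
|---|---|---|---|
| 10% / 10% | 5.5 + 0.44 − 0.66 | 5.28 | −0.22 (−4%) |
| 20% / 20% | 5.5 + 0.88 − 1.32 | 5.06 | −0.44 (−8%) |
| 20% / 10% | 5.5 + 0.44 − 1.32 | 4.62 | −0.88 (−16%) |
| 10% / 20% | 5.5 + 0.88 − 0.66 | 5.72 | +0.22 (+4%) |
| 30% / 10% | 5.5 + 0.44 − 1.98 | 3.96 | −1.54 (−28%) |
| 10% / 30% | 5.5 + 1.32 − 0.66 | 6.16 | +0.66 (+12%) |

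The last two rows keep 20% overall but put about 24 of 79 (0.3 × 79 = 23.7) in one group. The sign turns where 6.6 × ablation dropout = 4.4 × drug dropout, that is, where ablation dropout is two-thirds of drug dropout. The largest shift is 1.54 / 3.53 = 0.44 standard errors.

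**Month-6 scores carried forward, 20% / 20%.** Two time points do not show when the change occurs, so three cases are set out. With linear change over months 3 to 12, two-thirds is still to come at month 6: 4.40 for ablation and 2.93 for drug.
- Both groups have plateaued: 5.50
- Both change linearly: 5.5 + 0.2 × (2.93 − 4.40) = 5.21
- Ablation has plateaued, drug changes linearly: 5.5 + 0.2 × 2.93 = 6.09

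**Earlier scores.** The cases above are not bounds. A subject with only a screening score would be given a change of zero. If that applied to 20% of both groups, the planned 10-point difference would become 0.8 × 10 = 8.0, a shift of 2.0 / 3.53 = 0.57 standard errors.

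**Precision.** If all the dropout were withdrawals with carried scores and the SD stayed at 19.8, the nominal standard error would be 19.8 × √(2/79) = 3.15 instead of 3.53. That is about 11% smaller, with no 12-month information gained. The sample size calculation, by contrast, treats dropouts as supplying no data.

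**Recurrence, only if the clause is applied to it.** Assume constant hazard over months 3 to 12, uniform dropout over that time, and that recurrences recorded before withdrawal stay events. With true 12-month freedom S and dropout p, the reported rate is (1 − p) × S + p × (1 − S) / (−ln S).
- S = 0.80: 81.0% at p = 0.1 (+1.0 points); 81.9% at p = 0.2 (+1.9)
- S = 0.60: 61.8% at p = 0.1 (+1.8 points); 63.7% at p = 0.2 (+3.7)

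**The case against.** The strongest reply is that the effect is small and the evidence indirect. With equal 20% dropout the shift is 0.44 points, about an eighth of the planned standard error. Section 1 reports for pulsed field ablation that "at 6 and 12 months after surgery, the overall quality of life of patients (AFEQT and EQ-5D) increased by 5 points", which may indicate a plateau by month 6 in that group; if both groups plateau, month-6 scores carry no bias. The CABANA figures are whole-population visit means with 42.9% paroxysmal AF, not within-patient changes in persistent AF with HFpEF, and the protocol takes its planning values from the CABANA heart-failure cohort, for which it gives no month-3 score. The uneven splits are invented. The 20% dropout may include subjects eliminated under section 3.6, whose scores are not carried forward.

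All of this limits the size of the problem, and it stands. It does not support the rule. Section 1 gives no drug-group trajectory, and no figure in the protocol shows scores flat from month 1 or month 3. Nor can the rule be defended as conservative, because it enlarges the difference when enough more subjects leave the drug group.

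It is also fair to say that the recurrence figures depend on extending the clause to an endpoint it does not name, and that model details belong in the statistical analysis plan. But the carry-forward rule is stated in the protocol, so a plan that follows the protocol would inherit it.

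**Conclusion.** The concern holds. Section 3.7 fixes a single-value carry-forward for every withdrawn subject, and the only longitudinal two-group means in the protocol contradict the assumption behind it. The month-3 and month-6 scenarios shift a true difference of 5.5 by −1.54 to +0.66 points, each less than half the planned standard error; carried screening scores could shift it more. The bias is probably modest. With month-3 scores and equal dropout it shrinks the difference; with unequal dropout it can go either way, and the protocol gives no basis for knowing which.

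This rests on assumed dropout splits and timing, on leavers following their group mean, and on CABANA means standing in for this population. The recurrence figures are conditional on the clause being applied there. The change should be made, but the study does not fail without it.

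**What to change.** Delete the carry-forward clause in section 3.7 and keep the rest: records retained, withdrawn subjects in the full data set, reasons recorded.

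Analyse AFEQT change with a likelihood-based repeated-measures model on the scheduled baseline and 1-, 3-, 6- and 12-month scores. Make the 12-month contrast primary and add a sensitivity analysis for data not missing at random. Analyse recurrence by time-to-event methods, censoring event-free withdrawals at their last rhythm assessment. Model details can sit in the statistical analysis plan. Settle at the same time whether the pre-discharge AFEQT score in section 4.3 is collected.

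The cost is one clause of protocol wording and somewhat more modelling. The AFEQT scores and rhythm assessments are already scheduled, so no patients or visits are added and the sample size stays at 79 per group. The primary analysis would then rest on a missing-at-random assumption, which cannot be verified either; hence the sensitivity analysis.

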2.2 Research content

This study is a prospective, multicenter cohort study.

- (1) To observe the perioperative safety of pulsed field catheter ablation for patients with persistent atrial fibrillation and HFpEF;
- (2) To observe the improvement of cardiac function, the treatment effect and recurrence rate of atrial fibrillation in the pulsed field ablation group compared with the drug treatment group 1 month, 3 months, 6 months and 12 months after surgery;
- (3) To study the treatment strategy during the pulsed field ablation procedure, such as the correlation between ablation time, ablation site and the recurrence of atrial fibrillation and cardiac function after surgery, so as to guide better cryoablation strategies.

3. Study population

This study selected patients with persistent AF and HFpEF and divided them into a drug group (treated with class I or class III antiarrhythmic drugs) and a surgical group (Medtronic Pulse Select pulsed field ablation).

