The blank period starts from the day 0 when the patient receives Class I or Class III antiarrhythmic drugs, and the blank period of the drug group is from Day 0 to the next 90 days. During the blank period, patients can undergo electrical cardioversion to recover to sinus rhythm (if patients have recurrent atrial fibrillation during the blank period, they can choose to undergo electrical cardioversion again without the limit of countless times). Titration and adjustment of antiarrhythmic drugs are allowed during the blank period. In principle, no drug adjustments will be made after the blank period. Increasing the dose of the original Class I or Class III drugs or replacing antiarrhythmic drugs due to intolerance or drug side effects is considered the end point. Adding Class II or Class IV antiarrhythmic drugs for other reasons is allowed.

4.2 Treatment of patients in the surgical group::

4.2.1 Preoperative preparation:

(1) Class II and IV antiarrhythmic drugs, diuretics, digitalis drugs, etc. are allowed before surgery. The purpose is to control ventricular rate and improve heart failure treatment. The researcher can decide whether to continue taking the above-mentioned drugs;

(2) Anticoagulants, including warfarin and new oral anticoagulants, should not be discontinued before surgery. For warfarin, INR should be routinely tested before surgery;

(3) Complete preoperative examinations to exclude surgical contraindications (such as left atrial thrombus, abnormal coagulation function, severe thrombocytopenia, liver dysfunction, acute renal dysfunction, acute heart failure, etc.).

4.2.2 Intraoperative operation:

(1) General anesthesia;

(2) Heparin anticoagulation and maintaining ACT at 250-350 seconds;

(3) Single atrial septal puncture via femoral vein;

(4) Conventional PulseSelect PFA ring catheter preparation: flush the guidewire cavity, then insert the guidewire into the catheter through the guidewire Luer interface, retract the ring electrode into the introducer, slowly push the catheter slide control button forward to make the ring electrode linear, and at the same time push the introducer to retract the ring electrode. PulseSelect PFA ring catheter is inserted into the sheath.

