4.3 Clinical follow-up

(1) V1 screening period (-14 ~ 0 days)

If the patient has undergone relevant examinations before signing the informed consent form and within 14 days before surgery, these data can be collected as data for this clinical trial, and the patient does not need to undergo relevant examinations again. The following process should be completed:

- ◆ Sign the informed consent form;
- ◆ General information: date of birth, gender, height, weight;
- ◆ Vital signs: including blood pressure, heart rate/pulse, body temperature;
- ◆ Medical history: including hypertension, diabetes, coronary heart disease, stroke, allergies, surgical history, etc.;
- ◆ Inclusion criteria assessment;
- ◆ Laboratory tests;
- ◆ Standard electrocardiogram;
- ◆ AFEQT atrial fibrillation patient quality of life score sheet;
- ◆ Cardiac ultrasound;
- ◆ Medication status;
- ◆ Adverse events & serious adverse events;

(2) V2 Surgery (Day 0)

The following information should be collected/completed on the day of surgery:

- ◆ Medication status
- ◆ Adverse events & serious adverse events

(3) V3 Postoperatively (1-7 days, before discharge)

The following information needs to be collected/completed:

- ◆ Vital signs
- ◆ Laboratory tests
- ◆ Standard electrocardiogram
- ◆ AFEQT quality of life score for patients with atrial fibrillation
- ◆ Cardiac ultrasound

- ◆ Medication status
- ◆ Adverse events & serious adverse events

Post-discharge patient management recommendations:

Class I or Class III antiarrhythmic drugs can be used to maintain sinus rhythm within the 3-month window period after ablation or antiarrhythmic drugs.

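### Section 4.1 makes a drug change an end point, and names a 90-day blank period, for the drug group only; applied to the recurrence comparison, these rules would define failure differently in the two groups

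*Protocol*

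**What the plan says.** **Drug group (Protocol section 4.1).** Day 0 is the day the class I or III drug is received, and "the blank period of the drug group is from Day 0 to the next 90 days". Titration and repeat cardioversion are allowed in that time. Then: "In principle, no drug adjustments will be made after the blank period". The next sentence says that a dose increase of the original class I/III drug, or "replacing antiarrhythmic drugs due to intolerance or drug side effects is considered the end point". It does not say which endpoint is meant.

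**Surgical group (section 4.2).** No blank period is named and no event corresponding to the drug change is stated.

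**Both groups (section 4.3, post-discharge recommendations).** Class I/III drugs may be used "within the 3-month window period after ablation or antiarrhythmic drugs". This sentence permits drug use; it does not say which recurrences count.

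**Endpoints (section 5).** The primary endpoint is AFEQT change at 12 months. Secondary endpoint (1) is freedom from recurrence over the 12 months from surgery, "including atrial tachycardia (AT) lasting more than 30 seconds, atrial flutter (AFL), and AF endpoint events". It has no blanking and no drug-change component. Secondary endpoint (4) is "The incidence of AT/AF/AFL events 3 months later", with no group named.

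**Comparison (section 2.2, item 2).** The study will observe "the treatment effect and recurrence rate of atrial fibrillation in the pulsed field ablation group compared with the drug treatment group" at 1, 3, 6 and 12 months.

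**The concern.** Section 4.1 declares an end point that the protocol's own endpoint list does not contain, and declares it for one group. Centres act on section 4.1 during follow-up, so some may record a switch for side effects as an outcome event while others may not. The same section names a blank period for one group, while endpoint (1) starts counting at once.

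What is at stake is the between-group recurrence comparison. The study is described as a cohort study and no randomisation is stated, so the comparison already depends on measuring the outcome alike in both groups. Two distortions are possible, and they act in opposite directions:

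- If a drug change counts as failure, a patient in sinus rhythm who switches for tolerability fails in the drug group, with no equivalent route to failure after ablation. This leans against drug.
- If early recurrences are discounted only where a blank period is named, a patient whose only recurrence is early fails in the surgical group but not in the drug group. This leans against ablation.

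**Working it through.** **1. The texts side by side**

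| Rule | Drug group | Surgical group | Section 5 |
|---|---|---|---|
| Drug change is an end point | Yes (4.1) | Not stated (4.2) | In no endpoint |
| Named 90-day blank period | Yes (4.1) | Not stated (4.2) | Fits endpoint (4); absent from endpoint (1) |
| 3-month window for class I/III use | Yes (4.3) | Yes (4.3) | Not an outcome rule |

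The 1-month comparison in section 2.2 falls wholly inside the drug group's blank period. Section 4.1 does not expressly say that recurrences in the blank period are ignored. That is the usual meaning of the term, and the calculation below uses it.

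**2. The plan's sample size, used only to set n**

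Inputs from section 3.1: means 80.6 and 70.6, SD 19.8, two-sided alpha 0.05, power 0.80. The two-sample t-test gives 62.5, so 63 per group, with power 0.803 (protocol 0.80306). With 20% dropout, 63/0.80 = 78.75, so 79 per group and 158 in total. The stated figures reproduce. They concern AFEQT and do not depend on this point.

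**3. Size of the possible distortion**

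The protocol gives no rates for recurrence, drug change or early recurrence, so these are assumptions:

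- S = share recurrence-free under one common rule, equal in both groups: 60% (range 50-70%).
- q = share of those drug patients counted as failures for a drug change: 5, 10 or 20%.
- e = share of those surgical patients with an early-only recurrence that is counted: 5, 10 or 20%.

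Reported recurrence-free rates: drug = S(1 - q), surgical = S(1 - e). The test is the Pearson chi-square (section 9 names the chi-square test), two-sided 0.05, 63 per group, by exact binomial enumeration.

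| q | e | Drug | Surgical | Gap | Rejection rate |
|---|---|---|---|---|---|
| 0 | 0 | 60% | 60% | 0 | 5.6% |
| 5% | 0 | 57% | 60% | 3 points against drug | 7.1% |
| 10% | 0 | 54% | 60% | 6 points against drug | 11.6% |
| 20% | 0 | 48% | 60% | 12 points against drug | 29.4% |
| 10% | 10% | 54% | 54% | 0 | 5.8% |
| 20% | 5% | 48% | 57% | 9 points against drug | 19.0% |
| 5% | 20% | 57% | 48% | 9 points against ablation | 19.0% |

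Blanking alone (q = 0, e = 5, 10 or 20%) mirrors rows 2-4, with the gap against ablation. The patients reclassified are 63 x 0.60 x 0.05 = 1.9, 63 x 0.60 x 0.10 = 3.8 and 63 x 0.60 x 0.20 = 7.6.

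**4. Sensitivity**

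For one rule alone at 20%, the gap is 0.50 x 0.20 = 10 points if S = 50% (rejection 22.3%) and 0.70 x 0.20 = 14 points if S = 70% (38.1%). With 79 per group and S = 60%, one rule alone at 10% and 20% gives 11.3% and 31.6%, so the choice of n is not decisive.

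**5. The other meaning of the phrase**

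Section 3.7 provides for "Other circumstances that require the trial/trial treatment to be stopped", so the end point in 4.1 could mean the end of assigned treatment. The same section has the last evaluation of a withdrawn subject carried forward as the final result. If a drug change ended participation, that rule could supply the 12-month AFEQT value.

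**The case against.** The strongest reply is that the bias has to be imported. Endpoint (1) as written applies one arrhythmia-only rule, with no blanking and no drug-change component, to whoever is assessed. Section 2.2 does not invoke the 4.1 rules. Bias arises only if someone adds a 4.1 rule to the endpoint in one group, and the derivation of a secondary endpoint is commonly left to the SAP. The phrase may also be only a loose rendering of treatment failure or end of treatment.

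Much of this stands. Read literally, endpoint (1) has neither asymmetry. But the protocol does more than leave a detail open: it states a group-specific end point that its endpoint list does not contain, and an SAP would have to override or adopt it.

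Three stronger readings are tempting and are not supported:

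- A reader might infer that the blank period matches nothing in section 5. Endpoint (4) counts events after 3 months without naming a group, which fits a 90-day blank period. The conflict is with endpoint (1).
- A reader might infer that the surgical group has no 3-month window at all. Section 4.3 gives one to both treatments, though only to permit drug use.
- A reader might infer that the comparison is tilted towards ablation. The two rules push in opposite directions and can cancel.

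The magnitude is also fairly criticised: S, q and e are all assumed. The figures show how sensitive the comparison is, not what will happen.

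**Conclusion.** The point holds as an inconsistency that should be corrected. The drug-change end point in section 4.1 belongs to no listed endpoint and has no surgical counterpart. The blank period named for the drug group agrees with endpoint (4) but not with endpoint (1). If the 4.1 rules are applied as written to the recurrence comparison, the groups are judged by different failure rules.

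Under the assumed rates, either rule alone gives a false gap of 3-12 points at S = 60% and a rejection rate of 7.1-29.4%, against 5.6% with neither rule. With both in play, the net gap can lie anywhere from 12 points against drug to 12 points against ablation (10 to 14 points either way at the extremes if S is 50-70%).

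The reach is the secondary recurrence comparison. The AFEQT primary endpoint is unaffected unless the end point means the end of participation, in which case the carry-forward rule in section 3.7 could reach it. The text does not settle that, so neither a flat statement that AFEQT is safe nor one that it is compromised is justified. Confidence is medium because the meaning of the phrase is open.

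**What to change.** Reconcile sections 2.2, 4.1, 4.3 and 5.2:

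1. State that endpoint (1) and the section 2.2 recurrence comparison count only the AT, AFL and AF events that section 5 lists, with the same start-of-counting rule in both groups, measured from the start of assigned treatment.
2. State that a drug change under 4.1 does not count as a recurrence and does not end AFEQT follow-up.
3. Report drug changes separately and descriptively. Post-day-90 class I/III use should not be made a failure event counted alike in both groups: the drug group is defined by class I/III treatment, so most of its patients would meet it by design.
4. Have the sponsor state in 4.1 what the end point refers to. The phrase should be explained rather than simply deleted, since it may be a treatment-stopping rule. Nothing here changes how patients are treated.

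The cost is wording only. The flow chart notes and section 4.3 already require medication to be recorded from consent to the end of follow-up, so no new data are needed. The downside is that the apparent failure rate may fall in either group: in the drug group if switches no longer count, and in the surgical group if the common rule discounts early recurrences.
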